## F. Potential Benefits to Subjects

Participants in the interventional phase of the study may benefit as the use of TENS or mindfulness meditation and may experience improvements in a number of outcomes such as pain, quality of life, physical performance and physical activity. Furthermore, participants may become less reliant on pain medication, alcohol or substances for pain relief. The probability of such benefits is expected to be high in those in the TENS and meditation groups, with magnitude ranging from small improvements to large improvements that will vary by individual. The duration of such benefits may be prolonged if the participants continue with the use of TENS or meditation after the study concludes.

## 5.0 Special Considerations

### 5.1 Health Insurance Portability and Accountability Act (HIPAA)

We are not requesting a waiver of HIPPA authorization. All data from obtained in the study will be de-identified and linked only to the participant's study ID number, i.e. not health information or data will be linked to their name or other identifying information.

### 5.2 Family Educational Rights and Privacy Act (FERPA)

Not applicable.

### 5.3 Code of Federal Regulations Title 45 Part 46 (Vulnerable Populations)

#### A. Special Populations

- Not applicable.

### 5.4 General Data Protection Regulation (GDPR)

Not applicable.

### 5.5 NJ Access to Medical Research Act (Surrogate Consent)

Not applicable.

## 6.0 Data Management Plan

### 6.1 Data Analysis

Cross-sectional phase: We will test for baseline differences between those with painful DSP and those without painful DSP for the set of variables using independent t-tests (or Mann-Whitney tests if distributions are non-normal). Differences between those with and without DSP on potential demographic or clinical confounders will be adjusted for statistically.

Interventional phase: Assuming normality of the outcome variables of interest, between group repeated measures analysis of variance will be used to evaluate differences within and between groups for each outcome separately. In the case of non-normal outcome variable distribution, we will consider transforming the measure to normalize. If normalization is not warranted, then within group changes will be tested using a Friedman's test and between group differences will be compared descriptively. Data will be analyzed using both per-protocol and intention-to-treat analyses in the case of dropouts.

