#### B. Hypotheses / Research Question(s)

Hypothesis for Aim 1 (cross-sectional phase): Temporal and spatial characteristics of gait, walking endurance, physical performance scores and pain pressure threshold scores will be worse, and physical activity will be lower, in those with DSP than in those without DSP.

Hypothesis for Aim 2 (interventional phase): There will be a beneficial effect on all clinical and functional outcomes in each of the 2 intervention groups (mindfulness meditation; TENS) compared to a standard care group.

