## B. Data Points

Data elements include an array of non-invasive physical performance tests, physical activity monitoring, pain pressure threshold testing, and questionnaires. See Section 1.6 B. for detail on dependent variables/outcome measures.

The data elements will be collected at baseline (Week 0) for all participants.

At Week 0, all participants complete a demographic and health questionnaire and a physical activity questionnaire, the Brief Pain Inventory, and will undergo testing related to gait, walking endurance, physical performance, and pain-pressure threshold. They will receive a physical activity monitor that they will be asked to wear for 5 days and then ship back to the PI in a pre-paid shipping box.

Those with DSP-related pain will also complete questionnaires for pain, quality of life, depression and anxiety, catastrophizing behavior, and resilience at Week 0.

Those participants with DSP-related pain will be randomized to continue on to the interventional phase. Throughout the 6-week intervention period, participants in the TENS and MM groups will receive a daily text message in the morning that will ask them if they completed the home-based treatment on the day prior, and a weekly text message to ask if any problems have emerged; participants in the standard care group will receive a weekly text message to ask if any problems have emerged. All participants in the interventional phase will return for follow up testing after 6 weeks of intervention (Week 7), at which time all measurements taken at Week 0 will be repeated. In addition, participants will complete a satisfaction questionnaire at Week 7. They will once again receive a physical activity monitor that they will be asked to wear for 5 days and then ship back to the PI in a pre-paid shipping box. In addition, those who were randomized to the TENS or MM groups starting in March 2024 will complete a short follow up questionnaire at Week 15.

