#### 1.5 Sample Size Justification

A sample of 80 participants will be enrolled in the cross sectional phase and 40 participants (those with DSP) will continue on to the interventional phase.

The target sample size of 72 (36 with DSP and 36 without DSP) for the cross sectional phase is adequate to explore of between group differences in gait, physical performance, physical activity, and pain pressure threshold variables. For the interventional phase, 36 participants (12 participants in each of the 3 groups) is adequate to demonstrate feasibility and determine effect sizes that can inform a future randomized controlled trial. The expected accrual rate is 90% (drop-out rate of <10%); thus, the number enrolled will be 80.

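### Section 6.1 chooses the interventional analysis from the distribution of the outcome itself, but with two visits the group-by-time test depends on the distribution of within-arm change

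*Combined protocol and SAP*

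**What the plan says.** The rule is in Section 6.1, Data Analysis, under the interventional phase, and has three steps.

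1. The default: "Assuming normality of the outcome variables of interest, between group repeated measures analysis of variance will be used", applied to each outcome separately.
2. The first departure: "In the case of non-normal outcome variable distribution, we will consider transforming the measure to normalize".
3. The last resort, if normalization is judged unwarranted: "within group changes will be tested using a Friedman's test and between group differences will be compared descriptively".

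Both conditions refer to the outcome variable. Neither Section 6.1 nor any other section mentions residuals or change scores, names a normality test or threshold, or says which visit is examined or whether arms are pooled.

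Three other places matter. The Aim 2 hypothesis in Section 1.1 B is comparative: "There will be a beneficial effect on all clinical and functional outcomes in each of the 2 intervention groups", relative to standard care. Section 1.3 B fixes two measurement times, the second being the Week 7 visit, "at which time all measurements taken at Week 0 will be repeated". Section 1.5 gives the size: "36 participants (12 participants in each of the 3 groups) is adequate to demonstrate feasibility".

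**The concern.** The test that answers Aim 2 is the group-by-time interaction. With two visits it uses only each person's change, so a stable difference in level between people, however skewed, drops out. The stated condition examines the quantity that drops out.

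Two errors follow if the text is applied as written. An outcome that is skewed between people but changes symmetrically is moved off its original scale, or in the last resort gets no between-arm test, although the planned test was sound. Conversely, an outcome that looks normal at each visit but has a few outlying changes passes unnoticed.

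Sections 1.4 and 1.5 say the pilot is meant to supply effect sizes for later work. A needless transformation changes the scale on which an effect size is expressed, and a purely descriptive comparison leaves the Aim 2 hypothesis untested for that outcome.

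**Working it through.** **Inputs from the documents.** Three arms of 12 completers (Section 1.5) and two visits, Week 0 and Week 7 (Sections 1.3 B and 1.6 B). The only figure in the plan that can be reproduced is enrolment: 36/(1 − 0.10) = 40 and 72/(1 − 0.10) = 80. Both agree with Section 1.5 ("40 participants (those with DSP) will continue on to the interventional phase"; "The expected accrual rate is 90% (drop-out rate of <10%); thus, the number enrolled will be 80"). No alpha, SD, correlation or distribution is given for any outcome, and Section 1.4 says there are no preliminary data.

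**Step 1. What the test depends on.** Write the outcome of person i in arm g as Y(i,0) = u(i) + e(i,0) at Week 0 and Y(i,7) = u(i) + t + d(g) + e(i,7) at Week 7. Here u is the stable level, t the common time effect and d the arm effect. The change is

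D(i) = Y(i,7) − Y(i,0) = t + d(g) + e(i,7) − e(i,0).

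The level u(i) cancels. The group-by-time F is the one-way F on D, with 3 − 1 = 2 and 36 − 3 = 33 degrees of freedom. A numerical check on one simulated data set gave F = 1.2434 both ways.

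**Step 2. Skewed level, additive normal change.** Assumptions not in the documents: Shapiro-Wilk at 0.05, pooled over arms; an outcome counts as flagged if either visit fails; no treatment effect; 4,000 trials per cell. Entries are for within-person correlations 0.6 / 0.8 / 0.9.

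| Stable level | Raw values flagged | Change residuals flagged | Type I error, untransformed group-by-time test |
|---|---|---|---|
| Lognormal, log-SD 0.5 | 41 / 64 / 76% | 5 / 5 / 5% | 5.1 / 5.2 / 4.9% |
| Lognormal, log-SD 1.0 | 59 / 80 / 93% | 5 / 5 / 5% | 4.8 / 4.8 / 4.7% |
| Exponential | 53 / 80 / 92% | 5 / 4 / 5% | 5.9 / 5.0 / 4.8% |
| Two clusters | 47 / 98 / 100% | 5 / 5 / 6% | 5.2 / 4.5 / 4.9% |

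The Monte Carlo standard error of the type I error is √(0.05 × 0.95/4000) = 0.3 percentage points. Among flagged trials alone the error is 4.5 to 6.0%, so the flag does not mark trials in which the test fails. Using two visits inflates the flag rate only slightly: for truly normal data it would be at most about 1 − 0.95² = 9.75% if the visits were independent.

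**Step 3. What the transformation step rescues under additive change.** After a log transformation, shifted so that values are positive, 30 to 89% of all trials in Step 2 were flagged both before and after. The shift is crude, and a better-chosen transformation could do better. In a separate set with log-SD 0.35 to 0.7 and a one-SD-of-change effect in one arm, 28 to 58% of trials were flagged on raw values and significant on the untransformed test. Those still flagged after the log were 6 to 49%. Only this second group is at risk of losing the between-arm test.

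For scale, take a shift of 0.8 single-visit SD in one arm and correlation 0.8. The variance of change is 2 × (1 − 0.8) = 0.4, and the noncentrality is 12 × (2/3 × 0.8²)/0.4 = 12.8. Simulated power of the untransformed test is about 88%, the same overall and among flagged trials.

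**Step 4. Change proportional to level.** If change scales with level, the picture reverses. Across two sets of runs, change residuals were flagged in 20 to 72% and 28 to 88% of trials, so the residual check fires too, and rightly. A log transformation left only about 5 to 10% flagged, close to what normal data would give, and only 4 to 5% were both significant and still flagged. Here the plan's transformation step works: at the highest skew, power on the raw scale was 52 to 55%, while flagged-then-transformed trials gave a significant test in 60% of all trials.

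**The case against.** Four points can be made for the plan.

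**Transformation comes first.** A successfully transformed outcome keeps the repeated measures analysis and its between-arm test. A reader might infer that Section 6.1 discards the between-arm test whenever the raw data look skewed. The text does not say that: descriptive comparison is reserved for outcomes for which normalization is not warranted. This stands, and it means the raw flag rates are not rates of lost tests.

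**No mechanical trigger is stated.** Assuming a normal outcome is common shorthand for the model's error assumption, and the wording on transformation leaves room for judgement. Section 2.3 lists a statistician among the co-investigators, who may well look at residuals. This stands in part. The Shapiro-Wilk rule is a device for sizing the problem, not something the plan prescribes. But the written condition names the outcome variable twice and never the residuals.

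**The contrast depends on the data model.** Step 4 shows that under proportional change the gap narrows and the log step works. This stands in full. Several outcomes also have bounded scales or restricted entry (timed balance items capped at 10 seconds, foot pain of at least 3/10 at inclusion). That makes raw non-normality plausible, but their changes may be asymmetric too.

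**It is a pilot.** With feasibility and effect sizes as its purpose and no stated power, counting lost significant results is a harsh yardstick, and a descriptive comparison can still report arm differences. This limits the stakes. It does not answer the change of scale, which bears directly on effect sizes.

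**Conclusion.** The condition in Section 6.1 is attached to the wrong quantity. That follows from the algebra with two visits and needs no simulation. It concerns the group-by-time contrast only: the between-subject main effect does depend on the distribution of person averages, but it is not the treatment test.

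The size is uncertain because the documents give no distribution for any outcome. With Shapiro-Wilk at 0.05 and 12 per arm, skewed levels with additive normal change are flagged on raw values in roughly 40 to 90% of trials (up to 100% for two clusters), against about 5% on change residuals, while the untransformed test keeps its 5% level. With proportional change, residuals are flagged in about 20 to 90%, the log usually cures it, and the between-arm test is rarely lost.

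A reader might go further and infer that about half or more of this trial's outcomes will lose a valid test. The documents do not support that: they name no normality test and put transformation first, and nothing in them favours additive over proportional change. The supported conclusion is a rule that, followed literally, can needlessly change the effect-size scale or forgo a valid between-arm test, and can miss outlying changes. It should be corrected, and the correction is small.

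**What to change.** In Section 6.1, reword both conditions so that they refer to the residuals of the fitted repeated measures model, equivalently the within-arm Week 7 minus Week 0 change, assessed with residual and Q-Q plots. For example: the distributional assumption will be judged from plots of the model residuals; a transformation or another method will be used only if these residuals are clearly non-normal; where a transformed analysis is reported, the change on the original scale will be given for each arm alongside it.

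The cost is two reworded conditions and one added sentence. No extra data, visits or participants are needed, and the sample size is unaffected. The edit concerns when the plan leaves the default analysis; what the last-resort analysis should contain is a separate matter.

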
**Procedures to monitor subjects for safety and minimize risk of harm during the period of home-based interventions:** Participants in the interventional phase will be notified on baseline testing day that they should contact the PI if any problems arise during the 6 week at-home

intervention period. Participants in the TENS will be educated on how to inspect their skin after removing electrodes following a TENS treatment. Because DSP typically causes impaired sensation in the distal extremities TENS electrodes will not be placed on the feet. Rather, the locations will be more proximal at designated points on the lower extremities that have been assessed (on the day of baseline testing) by study personnel to have protective sensation as assessed with a 5.07 gauge (10 gram) Semmes-Weinstein monofilament. Participants in the TENS group who do not have protective sensation over the TENS sites in the legs will NOT be provided with TENS treatment. In addition, participants will be contacted once a week by text message meeting and will be asked if they are experiencing any problems or difficulties with the home-based interventions.

**Randomization:** The cross-sectional phase does not require randomization. For the interventional phase, participants with DSP will be randomly assigned to either the TENS group or the MM group or the standard care group (SC) using a web-based random number generator (<https://www.randomizer.org/>) that will link a group code (TENS, MM, or SC) to a participant's study ID number. Once a participant has been randomized to a group, the matching of the participant's ID number and assigned group will be delivered a study team member in a sealed opaque envelope.

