#### 1.4 Preliminary Data

There is no preliminary data; this is a new study. This interventional phase of this study will be used to generate data on the feasibility and effect sizes of the interventions that will be used for future projects.

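### Section 6.1 should report baseline-adjusted TENS–SC and MM–SC differences with intervals, and keep both comparisons for outcomes that stay non-normal

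*Combined protocol and SAP*

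**What the plan says.** The hypothesis for the interventional phase (section 1.1 B) is: "There will be a beneficial effect on all clinical and functional outcomes in each of the 2 intervention groups", each judged against SC. Section 1.4 says "There is no preliminary data; this is a new study". Section 1.5 takes 12 participants per arm as enough to show feasibility and "determine effect sizes that can inform a future randomized controlled trial".

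Participants with painful neuropathy are randomised to TENS, MM or SC. They return at Week 7, "at which time all measurements taken at Week 0 will be repeated" (section 1.3 B). The Week 15 questionnaire covers ongoing use of the interventions in the TENS and MM arms only (section 1.6 B), so it is not a third outcome time point.

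Section 6.1 gives the analysis in three steps:
- If outcomes are normal, "between group repeated measures analysis of variance will be used to evaluate differences within and between groups for each outcome separately".
- If an outcome is non-normal, a transformation is considered.
- If normalisation is judged not warranted, within-group change is tested by Friedman's test and "between group differences will be compared descriptively".

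On analysis sets it adds: "Data will be analyzed using both per-protocol and intention-to-treat analyses in the case of dropouts". Section 1.3 A describes a departure that is not a dropout. Members of the TENS group "who do not have protective sensation over the TENS sites in the legs will NOT be provided with TENS treatment".

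**The concern.** The hypothesis and the stated product of the pilot both call for two quantities: the TENS–SC difference and the MM–SC difference, each with its uncertainty. Section 6.1 names neither, mentions no interval, and does not adjust for the Week 0 value that is collected anyway. In the parametric branch an analyst could extract the two contrasts, but nothing requires it. In the last-resort non-normal branch the randomised comparison has no planned inference at all.

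The use of the pilot is what is at stake. A future trial would be planned from effect estimates whose intervals may be wider than they need be or, for outcomes that reach the last branch, may not be reported.

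**Working it through.** **Inputs.** From the documents: three arms, 12 completers per arm (36 in all), outcomes at Week 0 and Week 7. Assumed, because the documents do not give them: the correlation rho between the two visits and the ratio k of the Week 0 SD to the Week 7 SD. The Week 7 SD is set to 1. Intervals are two-sided 95%.

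**The plan's own figure.** With 10% dropout, 36/0.9 = 40 and 72/0.9 = 80, as section 1.5 states. The 36 and 72 are asserted and not derived from power or precision, so there is nothing further to reproduce.

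**The planned test is a change-score test.** With two visits, the group-by-time F equals the one-way ANOVA F on Week 7 minus Week 0. On simulated data with 3 × 12 participants both were 0.8900. The test has 2 df across three arms, so it is neither of the two hypothesised comparisons.

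**Half-width of the interval for one intervention versus SC.**
- Change score: t(0.975; 33) × √[(2/12)(1 + k² − 2·rho·k)], with t = 2.0345.
- ANCOVA: t(0.975; 32) × √[(2/12)(1 − rho²)(1 + 1/31)], with t = 2.0369. The factor 1 + 1/31 is the average cost of chance baseline imbalance, 1 + 1/(36 − 5).

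Example, rho = 0.5 and k = 1: change score 2.0345 × √(0.1667 × 1.000) = 0.83; ANCOVA 2.0369 × √(0.1667 × 0.774) = 0.73. That is 12% narrower.

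| rho | Change, k = 1 | ANCOVA | Effect of ANCOVA, k = 1 | Effect of ANCOVA, k = 0.7 |
|---|---|---|---|---|
| 0.3 | 0.98 | 0.81 | 18% narrower | 6% narrower |
| 0.5 | 0.83 | 0.73 | 12% narrower | 1% narrower |
| 0.7 | 0.64 | 0.60 | 6% narrower | 1.7% wider |
| 0.8 | 0.53 | 0.51 | 3.5% narrower | 0.3% wider |
| 0.9 | 0.37 | 0.37 | 1% narrower | 7.5% narrower |

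**Worst case.** A change score fixes the baseline slope at 1; ANCOVA estimates it, with true value rho/k. At k = rho the true slope is 1 and the change variance, 1 + rho² − 2·rho², equals 1 − rho². Only the cost of estimation is left: √(32/31) × 2.0369/2.0345 = 1.017, a loss of 1.7%. This is an average. In 20,000 simulated trials at rho = k = 0.8, the ANCOVA interval was more than 1.7% wider in about 47%, and the 95th percentile of the loss was just under 7%.

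**Validity at this size.** In simulation with 12 per arm, type I error of the adjusted contrast was 0.043 to 0.051 under normal, lognormal and ceiling-limited outcomes. For rank ANCOVA it was 0.047 to 0.052.

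**Non-normal branch.** With two visits, no ties and n = 12, Friedman's statistic is (n₊ − n₋)²/12, which is a sign test within one arm.
- 10 against 2: 64/12 = 5.33, p = 0.021 (exact sign test 0.039).
- 9 against 3: 36/12 = 3.0, p = 0.083.

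At least 10 of 12 must therefore change in the same direction. Suppose all three arms truly improve by the same assumed d = 0.25, 0.5, 0.75 or 1.0 SD of change. Each arm is then significant for improvement with probability q = P(Binomial(12, Φ(d)) ≥ 10) = 0.082, 0.233, 0.466 or 0.706. The chance that at least one intervention arm is significant and SC is not is [1 − (1 − q)²](1 − q) = 14%, 32%, 38% or 27%. Within-arm tests cannot stand in for the comparison with SC.

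**The case against.** The planned ANOVA is valid, and the two contrasts with SC can be drawn from it. That stands. A reader might infer that the analysis is wrong or cannot answer the hypothesis, and the documents do not support that. The gain from ANCOVA depends on rho and k, which are unknown. Entry requires average foot pain of at least 3/10 (section 4.1 C), so a restricted Week 0 range is plausible for pain, and there the gain may vanish. This limits the precision argument. It does not touch the case for naming the contrasts and their intervals.

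A reader might also infer that any non-normal outcome goes straight to description. It does not: transformation is considered first, and the gap opens only where it is not used. Nor does section 6.1 propose to read significance in one arm and not in SC as evidence of effect. The 14% to 38% figures show why the within-arm tests are no substitute, and are not a prediction of how the authors would report.

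Changing a model late carries its own risk. Data analysis runs throughout the study (section 1.10), and Week 7 data are reviewed within 24 hours for safety (section 6.3 A). This objection stands and shapes the fix.

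Last, an analysis of observed Week 7 values leaves out dropouts, whom section 6.1 promises to cover by intention-to-treat. This also stands, so such an analysis cannot be the only one.

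**Conclusion.** The point holds as a recommended change. Section 6.1 compares arms by a valid but generally less precise change-score analysis, through an omnibus test that matches neither hypothesised comparison. Its last-resort branch gives the randomised comparison no inference. The second gap rests on the text alone.

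The size of the precision gain rests on assumed rho, equal SDs, normal theory and a common slope: about 18%, 12%, 6% and 1% at rho 0.3, 0.5, 0.7 and 0.9. The expected loss is at most about 1.7%, but a reader should not take that as a ceiling for this one trial. Even adjusted, the half-width is about 0.6 to 0.8 SD for rho from 0.7 down to 0.3, so the results are pilot estimates and not efficacy tests.

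Two further inferences are not supported. The documents do not say how many people assigned to TENS are not given it, and the number could be zero, so no dilution of the TENS–SC difference can be stated. The absence of a ranking between per-protocol and intention-to-treat is missing detail and not an error.

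**What to change.** In section 6.1, for each outcome measured at both Week 0 and Week 7:

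1. Fit an ANCOVA of the Week 7 value on arm and Week 0 value. Report the TENS–SC and MM–SC adjusted differences with 95% intervals as pilot estimates. Satisfaction, adherence and the Week 15 questionnaire stay descriptive.
2. For outcomes that stay non-normal, keep the same two contrasts (ANCOVA, with rank ANCOVA as a check) in place of within-arm Friedman tests alone.
3. Analyse participants as randomised, including anyone assigned to TENS but not given it. State that using observed Week 7 data only is an available-case analysis, and keep an analysis that includes dropouts so that the intention-to-treat promise is met. Define per-protocol.
4. Date the change and state whether outcome data by arm had already been seen. If so, report the currently planned ANOVA alongside.

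Minimum version if the ANOVA is kept: report the two change-score contrasts with 95% intervals, for non-normal outcomes too.

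The cost is a dated rewording of section 6.1, with the same data, visits and standard software. The statistical price is one error degree of freedom and the small expected loss described above when rho is high or the Week 0 range is restricted. Testing was scheduled from May 2022 and the protocol is at v10.0 of 3.1.2024, so the change cannot be presented as specified before data collection.

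### For interventional outcomes that stay non-normal, section 6.1 tests only change within each arm and leaves the randomised comparison with standard care untested

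*Combined protocol and SAP*

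**What the plan says.** Section 1.1 B states the Aim 2 hypothesis as a beneficial effect on all outcomes "in each of the 2 intervention groups (mindfulness meditation; TENS) compared to a standard care group". Section 1.3 A randomises participants to three arms. Section 1.3 B places the repeat assessment at Week 7, "at which time all measurements taken at Week 0 will be repeated", so these outcomes have two time points.

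Section 6.1 then gives two routes for interventional outcomes:

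- **Normal outcomes:** "between group repeated measures analysis of variance will be used to evaluate differences within and between groups".
- **Non-normal outcomes:** a transformation is considered. If normalising is judged not warranted, "within group changes will be tested using a Friedman's test and between group differences will be compared descriptively".

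For the cross-sectional phase, the same section keeps a between-group test when normality fails: "or Mann-Whitney tests if distributions are non-normal".

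On purpose, section 1.4 says the interventional phase will "generate data on the feasibility and effect sizes of the interventions", and section 1.5 says 12 per arm is adequate to "determine effect sizes that can inform a future randomized controlled trial".

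**The concern.** On the non-normal route, significance testing is kept but pointed at change within each arm. The randomised contrast, which is what the hypothesis concerns, is left to description with no between-arm estimate or interval named. The ANOVA route does evaluate differences between groups, although it too names no pairwise estimate or interval. What is particular to the fallback is that the between-group test disappears.

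Within-arm change mixes any treatment effect with everything SC participants also experience, such as regression to the mean, practice on the tests and the natural course. It cannot supply the effect size that sections 1.4 and 1.5 want for a later trial. If readers compare the three within-arm p-values, an intervention arm that is significant beside an SC arm that is not will look like evidence of benefit. That pattern can arise often when the arms do not differ.

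**Working it through.** **Inputs from the protocol.** Three arms, 12 completers each (1.5); two time points, Week 0 and Week 7 (1.3 B). The stated enrolment reproduces: 36/(1 − 0.10) = 40 for the interventional phase and 72/(1 − 0.10) = 80 overall. No significance level, power or effect size is given, so there is no power calculation to reproduce.

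**Assumptions.** Two-sided 0.05. The share of participants improving is the same in every arm, so there is no treatment effect. The documents do not give this share, so a range is shown.

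**What Friedman's test does here.** With two time points the statistic is (improved − worse)² / (improved + worse), referred to chi-square on 1 df. It uses only the direction of change, not its size. With 12 participants and no ties:

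- 10 of 12 one way: (10 − 2)²/12 = 5.33, p = 0.021 (exact sign test 0.039).
- 9 of 12 one way: (9 − 3)²/12 = 3.00, p = 0.083 (exact 0.146).

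An arm is therefore significant only if at least 10 of 12 move in the same direction.

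**How often the arms disagree when they do not differ.** Let u be the binomial probability that an arm is significantly improved, and a the probability that it is significant in either direction. Then:

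- a given intervention arm significantly improved, SC not significant: u(1 − a)
- at least one of the two intervention arms so: (1 − (1 − u)²)(1 − a)

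| Share improving in every arm | u | One given arm | At least one of two |
|---|---|---|---|
| 50% | 0.019 | 1.9% | 3.7% |
| 60% | 0.083 | 7.6% | 14.6% |
| 70% | 0.253 | 18.9% | 33.0% |
| 80% | 0.558 | 24.7% | 35.6% |
| 90% | 0.889 | 9.9% | 11.0% |

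Worked line for 70%: a is also 0.253, so 0.253 × 0.747 = 0.189, and (1 − 0.747²) × 0.747 = 0.330.

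If each participant has a 25% chance of no change, and 60, 70 or 80% of the rest improve, one given arm gives 7, 16 or 25% with the chi-square p-value and 4, 11 or 22% with the exact one. At least one arm gives 13, 29 or 38% and 8, 21 or 37%. These figures depend only on direction of change, so they need no normality assumption.

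**Whether a between-arm rank analysis works at this size.** Simulated at 12 against 12, with differences in SD of change:

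| Change distribution | Power at 0.05, d = 0.5 / 0.8 | Power at 0.025, d = 0.5 / 0.8 | Median half-width, 95% / 97.5% interval |
|---|---|---|---|
| Normal | 20 / 43% | 13 / 33% | 0.88 / 1.00 SD |
| Laplace | 27 / 55% | 19 / 45% | 0.76 / 0.87 SD |
| Exponential | 37 / 66% | 27 / 56% | 0.66 / 0.77 SD |

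Coverage of the Hodges-Lehmann interval was 0.954 to 0.956 at 95% and 0.975 to 0.977 at 97.5%. With the SC arm shared, the chance of at least one false rejection over the two comparisons was 0.081 to 0.083 at 0.05 each and 0.045 at 0.025 each.

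**Heavily tied scores.** With assumed changes of −1/0/1/2 at probabilities 0.10/0.50/0.25/0.15 in both arms, the 95% Hodges-Lehmann interval covered 0.999 and had an endpoint at zero in 57% of trials. For the probability of greater improvement, a Brunner-Munzel interval covered 0.947 and a percentile bootstrap 0.935.

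**The case against.** The best defence is that this is a pilot. Twelve per arm is justified by feasibility and effect sizes, not by testing, and a descriptive comparison can include between-arm effect sizes. This has force: the plan does not rule out reporting them, and a wholly descriptive pilot would be coherent. But this plan is not wholly descriptive. It states a comparative hypothesis, keeps significance tests, and on this branch spends them on a different question while committing to no between-arm estimate.

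Second, the disagreement rates describe an inference the protocol never states, and they depend on an assumed share improving. Both are true. At 50 to 60% improving, the rate for one given arm is only 1.9 to 7.6%. The higher rates need 70 to 80% of SC participants to improve, which nothing in the documents establishes for a group continuing its usual management. The figures show what could follow if the only available p-values were read side by side. They are not an error rate of a stated decision rule.

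Third, the remedy makes p-values optional although the missing item is a between-group test. The interval answers this: a Hodges-Lehmann interval is itself between-arm inference and agrees with the rank-sum test at the same level.

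Finally, Aim 1 compares two groups once, whereas Aim 2 has three arms and two time points. The Mann-Whitney contrast is therefore not an internal contradiction. It does show that the plan accepts rank tests between groups elsewhere.

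**Conclusion.** The concern holds and is minor. Followed as written, section 6.1 gives inference on within-arm change for persistently non-normal outcomes and none on the comparison with SC; no other section supplies it. How many outcomes take this route is unknown. If the within-arm results were compared informally, a false impression of benefit from at least one intervention could arise in roughly 4 to 36% of trials per outcome across the shares tabulated without ties. That range assumes 12 completers per arm, two-sided 0.05, no treatment effect and an equal share improving in every arm. The absence of a between-arm analysis on this branch depends on none of these assumptions.

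**What to change.** In 6.1, replace the fallback with a between-group rank analysis of Week 0 to Week 7 change for two named contrasts, TENS against SC and MM against SC:

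- **Main result:** the Hodges-Lehmann difference with a 95% interval.
- **P-values, if reported:** the exact or permutation rank-sum test at 0.05, labelled exploratory, so that test and interval agree. If error control over the two contrasts is wanted, use 97.5% intervals with p at 0.025. Mixing a 95% interval with p at 0.025 gave conflicting answers in 10.0% of simulated trials (normal changes, d = 0.8).
- **Heavily tied ordinal scores:** also report the probability of greater improvement with a Brunner-Munzel or bootstrap interval. Choose one in advance. Both can fall slightly short of nominal: 0.936 and 0.928 in simulations with one arm shifted.
- **Within-arm changes:** may still be shown, but not as evidence of benefit over SC.
- **Consistency:** name the same two contrasts, with intervals, on the ANOVA route.

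The cost is a few sentences and no new data. The drawback is low power and wide intervals at 12 per arm, so the estimate and its interval, not the p-value, should carry the result.
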